29.1 Pre-specified mechanistic endpoints (supportive)

Exploratory mechanistic outcomes (e.g., anaerobic capacity, systemic biomarkers including inflammatory markers and per- and polyfluoroalkyl substances) will generally be analyzed using the same model framework as in Section 27

29.2 High-dimensional discovery analyses (omics)

Untargeted proteomic and metabolomic data will be processed using current best-practice pipelines (e.g., DIA-NN, Spectronaut, and/or established R-based workflows). Statistical methods (e.g., moderated t-tests/linear models [LIMMA], empirical Bayes approaches, or mixed models where repeated measures are available) will be selected based on data dimensionality, variance structure, and diagnostics. Multiplicity in omics analyses will be addressed using false discovery rate (FDR) control (e.g., Benjamini–Hochberg), and findings will be reported as hypothesis-generating.

29.3 Genetic and effect-modification analyses (exploratory)

Pre-specified candidate polymorphisms will be evaluated as potential effect modifiers of statin and/or exercise responses. Models may include genotype (e.g., allele dosage) and its interaction with group × time terms; subgroup summaries (e.g., carriers vs non-carriers) may be presented where allele frequency permits. Results will be interpreted as exploratory with multiplicity control (e.g., FDR) applied where appropriate.

29.4 Sex-dependent analysis (exploratory)

Potential sex differences will be explored by extending the primary model to include a group × time × sex interaction. These analyses are intended to describe potential heterogeneity of response and will be interpreted as hypothesis-generating.

30. Harms

Adverse events (AEs), including statin-associated muscle symptoms (SAMS), will be monitored prospectively from intervention initiation (first dose and/or first supervised training session) until the post-intervention visit (V2).

All reported events will be summarized descriptively by intervention group according to:

- **Frequency** (number and percentage of participants reporting ≥1 AE),
- **Severity** (mild, moderate, severe)
- **Assessed relationship to study intervention** (related, possibly related, unrelated).

Pre-specified questionnaires (e.g., a structured SAMS symptom inventory) will supplement spontaneous reports to ensure standardized data collection. Serious adverse events (SAEs) and withdrawals due to AEs will be listed individually and summarized by category.

Safety summaries will be based on the Safety population (participants with ≥1 exposure to the allocated intervention; consistent with the ITT definition). If sample size permits, exploratory subgroup summaries (e.g., by sex or adherence status) may be presented to describe patterns in AE reporting; no formal hypothesis testing is planned for safety endpoints.

31. Statistical software

Primary and confirmatory analyses will be conducted in R (version ≥ 4.0). Python (version ≥ 3.10) may be used for supportive analyses, data processing, and independent verification where appropriate. Exact software and package versions used for the final locked analysis will be documented in the analysis log and/or supplementary materials.

References

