This Statistical Analysis Plan (SAP) supplements the main study protocol and prespecifies analyses for all primary, secondary, and exploratory outcomes. This amended version was finalized prior to database lock and unblinding, and follows contemporary guidance for SAP content in clinical trials (Gamble *et al.*, 2017).

Signature Page

We, the undersigned, approve and will adhere to the Statistical Analysis Plan detailed herein:

SAP authors

| Name | Title | Role | Signature | Date |
|--|-------|--|--|---------------------|
| [name] ¹ | PhD | Sponsor- investigator; SAP co-author |  | 21 February 2026 |
| [name] ² | PhD | SAP co-author |  | 21 February 2026 |

¹Faculty of Health, University of the Faroe Islands, Tórshavn, Faroe Islands

²Department of Biomedical Sciences, University of Copenhagen, Copenhagen, Denmark

Section 2: Introduction

7. Background and Rationale (adapted from the published protocol)

Detailed background and rationale are presented in the published protocol (Sjúrðarson *et al.*, 2025). In brief, statins are first-line therapy for dyslipidaemia but have been hypothesized to attenuate exercise-induced improvements in skeletal-muscle mitochondrial content and function as well as cardiorespiratory fitness (Mikus *et al.*, 2013). This trial is designed to quantify the exercise × statin interaction on mitochondrial function and related physiological and clinical markers in middle-aged adults with dyslipidaemia, using citrate synthase (CS) maximal activity as a validated biomarker of mitochondrial content/oxidative capacity and peak oxygen uptake (VO_{2peak}) as a complementary integrated marker of whole-body fitness. The central scientific question is whether concomitant high-dose atorvastatin attenuates adaptations normally observed with supervised high-intensity interval training.

8. Objectives

Overall objective. To estimate the individual and combined effects of 12 weeks of atorvastatin and supervised exercise training on physiological, biochemical, and patient-reported outcomes in adults with dyslipidaemia.

Primary objective.

To evaluate the effect of 12 weeks of atorvastatin, exercise training, and their combination on skeletal-muscle CS maximal activity across all four intervention groups.

The main mechanistic contrast of interest is Exercise + Placebo vs Exercise + Atorvastatin, testing whether atorvastatin blunts training-induced mitochondrial adaptations.

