Additional pre-specified pairwise comparisons among the four groups will be analyzed to fully characterize exercise, drug, and combined effects (see Section 12).

Key secondary objective.

To evaluate changes in VO_{2peak} ($\text{mL}\cdot\text{kg}^{-1}\cdot\text{min}^{-1}$) across the four groups, with the same principal contrast (Exercise + Placebo vs Exercise + Atorvastatin), testing whether atorvastatin blunts training-induced adaptations in VO_{2peak} .

For details on outcome selection and rationale, see the published protocol.

Section 3: Study Methods

9. Trial design

This investigator-initiated, randomized, double-blinded (medication) and placebo-controlled trial evaluates the effects of high-dose atorvastatin and supervised high-intensity interval training (HIIT), alone or combined, over 12 weeks in adults with dyslipidaemia. Participants are allocated to one of four parallel arms:

1. Exercise + Placebo
2. Exercise + Atorvastatin
3. No Exercise + Atorvastatin
4. No Exercise + Placebo

Medication allocation is double-blinded (participants and investigators). Exercise allocation cannot be blinded to participants or trainers; however, outcome assessors and laboratory personnel will remain blinded to medication allocation, and data analysts will remain blinded to both medication and exercise allocation until database lock.

Interventions

- **Wash-out:** 4-week discontinuation of lipid-lowering therapy before baseline (week 0).
- **Medication:** Atorvastatin 40 mg (Week 1-2), then 80 mg daily; matching placebo in placebo arms.
- **Exercise:** Supervised high-intensity interval training (HIIT) three times per week, performed at or above 90 % of maximal aerobic power (MAP), with intensity monitored using power output (wattage), heart rate (HR), and ratings of perceived exertion (RPE).
- **Non-exercise arms:** Maintain habitual physical activity.

Study visits:

V0 = Screening, V1 = Baseline (all measurements completed before randomization), Week 6 = mid-intervention blood samples and questionnaires, V2 = Post-intervention (12 weeks).

10. Randomization

Randomization uses a computer-generated list prepared by an independent statistician. Allocation is performed by a non-involved colleague after completion of baseline assessments. Participants are randomized in a 60:40 exercise:non-exercise ratio to achieve approximately:

| Group | n |
|-----------------------------------|----------|
| Exercise + Placebo | 36 |
| Exercise + Atorvastatin | 36 |

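### Section 30 rates adverse events against one undivided study intervention, so 'related' is ambiguous in the exercise arms and not comparable with the non-exercise arms

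*SAP*

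**What the plan says.** SAP Section 30 (Harms) starts adverse event monitoring at "first dose and/or first supervised training session", so within that section the word intervention covers two components. It continues: "All reported events will be summarized descriptively by intervention group according to" three items, namely frequency, severity and causality. Frequency has a counting unit, "number and percentage of participants reporting ≥1 AE". The causality item is "Assessed relationship to study intervention", with three grades, no split by component and no counting unit. Serious events and withdrawals due to adverse events are also listed individually, a structured inventory of statin-associated muscle symptoms (SAMS) supplements spontaneous reports, and no safety testing is planned.

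Section 9 gives the components. For medication it is atorvastatin, or "matching placebo in placebo arms"; for exercise it is "Supervised high-intensity interval training (HIIT) three times per week". The non-exercise arms keep their habitual activity. Medication is double-blind, while exercise cannot be blinded to participants or trainers. Section 11 gives 36 randomised per exercise arm and 24 per non-exercise arm. The overall objective in Section 8 is "To estimate the individual and combined effects of 12 weeks of atorvastatin and supervised exercise training".

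**The concern.** One rating is asked to cover two exposures that only some arms share. In an exercise arm, an event blamed on training and an event blamed on the tablet receive the same code. In a non-exercise arm the code can refer only to the tablet. A reader who compares 'related' events across the four columns is then comparing different quantities.

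Elsewhere the SAP keeps the components apart: Sections 19–20 define medication adherence and exercise adherence separately, and Section 9 gives the two components different blinding. The causality line is where they merge. At stake is whether the harms table can speak to the individual effects named in the overall objective, and whether drug tolerability in the exercise arms can be read from the 'related' row.

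**Working it through.** The SAP states no figure for this row, so there is none to reproduce. The check is mainly a comparison of text, with an illustration of size.

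**1. Meaning of 'related' by arm (Sections 9, 11 and 30)**

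| Arm | n | Tablet | Training | 'Related' can mean |
|---|---|---|---|---|
| Exercise + Placebo | 36 | yes | yes | tablet, training or both |
| Exercise + Atorvastatin | 36 | yes | yes | tablet, training or both |
| No Exercise + Atorvastatin | 24 | yes | no | tablet |
| No Exercise + Placebo | 24 | yes | no | tablet |

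The meaning is ambiguous in 36 + 36 = 72 of 120 participants and unambiguous in 24 + 24 = 48.

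**2. Dilution between the two exercise arms, if counted per participant**

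Let e be the share with a training-related event, equal in both exercise arms, and d the share with a tablet-related event, independent of e. Then

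P(any related) = 1 − (1 − e)(1 − d), and the difference between arms = (1 − e)(d_atorvastatin − d_placebo).

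All rates below are assumptions; the SAP gives none.

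| d, placebo vs atorvastatin | e | Any related, placebo vs atorvastatin | Difference (points) | Difference if rated for the tablet alone |
|---|---|---|---|---|
| 5% vs 15% | 30% | 33.5% vs 40.5% | 7 | 10 |
| 5% vs 15% | 40% | 43.0% vs 49.0% | 6 | 10 |
| 5% vs 15% | 50% | 52.5% vs 57.5% | 5 | 10 |
| 5% vs 20% | 20% | 24% vs 36% | 12 | 15 |
| 5% vs 20% | 40% | 43% vs 52% | 9 | 15 |
| 5% vs 20% | 60% | 62% vs 68% | 6 | 15 |

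The difference shrinks by the factor (1 − e) but keeps its sign.

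**3. If events are counted instead**

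A tablet-related event then adds to the count even in someone who already has a training-related event. If training-related events are equally common in both arms, they cancel in the expected difference. The dilution in step 2 therefore depends on a counting unit that Section 30 does not fix for this row. The ambiguity in step 1 does not.

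**4. Precision of a descriptive medication comparison (assumed 20% incidence in both groups)**

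Half-width of the 95% CI = 1.96 × √(2 × 0.2 × 0.8 / n):

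- 36 vs 36: 1.96 × √(0.32/36) = 18.5 points
- 24 vs 24: 1.96 × √(0.32/24) = 22.6 points
- 60 vs 60, stratified by exercise with weights 0.6 and 0.4: variance = 0.36 × 0.32/36 + 0.16 × 0.32/24 = 0.00533, half-width 14.3 points

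**The case against.** A reader might infer that harms blamed on training hide harms of atorvastatin in the arms of the main contrast. The SAP does not support that. Both exercise arms are assigned the same training, medication is double-blind, and frequency and severity are summarised by randomised arm. An excess of events in Exercise + Atorvastatin over Exercise + Placebo therefore estimates the drug's added harm without any causality judgement.

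SAMS, the harm most easily confused with the effects of training, does not depend on this row. It has its own inventory (Section 30) and is a secondary outcome (Section 26), and Sections 16–18 promise between-group differences with 95% confidence intervals for all outcomes. It would be wrong to say that no drug-specific harm gets an interval; adverse event incidence is what lacks one.

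The size is also uncertain. The rates are assumed, the participant-level count is attached only to frequency, and a loss of 3 to 5 points is small beside a half-width of 18.5 points for 36 against 36.

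Finally, the protocol is not at hand and may rate causality for each component. That bears on whether records need re-rating. It does not change the fact that the SAP, which decides the table, specifies one undivided line.

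All of this stands and limits the point to the causality row. It does not remove the ambiguity there. The SAMS inventory covers muscle symptoms only, and for other events the SAP specifies no attribution by component.

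**Conclusion.** The point holds as a minor reporting defect. That 'related' has one meaning in 48 participants and up to three in the other 72 follows from the text without assumptions. Dilution of the contrast between the exercise arms is conditional on a participant-level count and on assumed, independent rates; under those shown it removes 3 to 9 points from a true difference of 10 or 15. It is dilution, not concealment.

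A reader might also infer that leaving out a pooled atorvastatin against placebo comparison is an error. It is not. The trial is laid out as four parallel arms, its central question is whether drug and exercise interact, and the pooled counts can be formed from the four-arm table. Pooling is an optional gain in precision.

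**What to change.** In Section 30, replace the single causality line with two:

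- relationship to study medication, for all four arms, rated blind to medication allocation;
- relationship to exercise training, for the exercise arms only (not applicable elsewhere).

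Allow an event to be related to both, tabulate the two separately by arm, and state whether the rows count events, participants or both. If only a joint rating was recorded, which the SAP cannot show, re-rate those records before unblinding.

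Optionally, beside the retained four-arm table, add a descriptive risk difference for atorvastatin against placebo (60 vs 60), stratified by exercise allocation, with a 95% CI and no p-value. It should carry the caveat that statin harms may differ by exercise, and it does not replace the split rating, since a count of any adverse event still mixes both causes.

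The cost is a change of SAP wording, a little investigator time if re-rating is needed, and one extra table. No efficacy analysis changes.

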For all outcomes, we will report within-group estimated mean changes (V2–V1) and between-group differences in change (contrasts of V2–V1), each with 95% confidence intervals (CIs). Analyses will be two-sided and performed using $\alpha = 0.05$. Multiplicity will be controlled for the primary endpoint (six tests) using the Holm–Šidák procedure, maintaining a familywise two-sided $\alpha = 0.05$. For all other secondary and exploratory outcomes, confidence intervals and p-values will not be adjusted for multiple testing.

19–20. Adherence, Protocol Deviations, and Analysis Populations

Analysis Populations

Intention-to-Treat (ITT) – primary analysis set

All randomized participants will be included in the primary analyses and analyzed according to their allocated intervention group, irrespective of intervention initiation, adherence, or protocol deviations.

Per-Protocol (efficacy under adherence):

Participants without major protocol deviations who (i) complete V1 and V2 assessments and (ii) meet adherence criteria for their assigned intervention(s):

- Medication arms: $\geq 75\%$ of planned doses at assigned dose (80 mg; 40 mg if medically indicated).
- Exercise arms: $\geq 75\%$ session attendance and $\geq 75\%$ of prescribed high-intensity interval time performed at $\geq 90\%$ maximal aerobic power (MAP).

Adherence definitions and quantification

Medication adherence (%): (doses taken / doses planned) × 100; sources: medication logs + pill count.

Exercise adherence:

- **Session attendance (%):** (sessions attended / sessions prescribed) × 100 (3 sessions/week planned).
- **Intensity adherence (%):** (completed high-intensity interval time at ≥90% MAP / prescribed high-intensity interval time) × 100. MAP is defined as the lowest cycling power output eliciting VO_{2peak} during the incremental test. Primary source: power output; HR as backup. If session-level data are missing, within-participant imputation from temporally adjacent sessions in the same phase may be used.

Protocol Deviations

Major deviations include prohibited medications, <75% adherence to allocated medication/exercise criteria, withdrawal of consent, or non-attendance of V2 testing. All deviations will be listed and summarized by intervention group.

Section 5: Trial Population

21. Screening data

Screening and enrolment figures will be summarized in the CONSORT flow diagram.

Individual-level screening data will not be reported.

22. Eligibility criteria

Inclusion criteria:

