| Variable | Total (n =) | Exercise + Atorvastatin | Exercise + Placebo | No Exercise + Atorvastatin | No Exercise + Placebo |
|--------------------------|-----------------|----------------------------|-----------------------|----------------------------------|--------------------------|
| Demographics | | | | | |
| Sex (M/F) (n (%)) | | | | | |
| Age (years) | | | | | |
| Anthropometry | | | | | |
| Height cm | | | | | |
| Weight kg | | | | | |
| BMI kg·m ⁻² | | | | | |
| Waist circumference (cm) | | | | | |
| Hip circumference (cm) | | | | | |
| Body fat (%) | | | | | |
| Lean mass (kg) | | | | | |

| | | | | | |
|--|--|--|--|--|--|
| Cardiorespiratory | | | | | |
| VO _{2peak} (mL·min ⁻¹) | | | | | |
| VO _{2peak} (mL·kg ⁻¹ ·min ⁻¹) | | | | | |
| Resting heart rate (BPM) | | | | | |
| Systolic BP (mmHg) | | | | | |
| Diastolic BP (mmHg) | | | | | |
| Metabolic profile | | | | | |
| Fasting glucose (mmol/L) | | | | | |
| HbA _{1c} (mmol/mol) | | | | | |
| Fasting insulin (pmol/L) | | | | | |
| Fasting c-peptide (pmol/L) | | | | | |
| HOMA-IR | | | | | |
| Lipids (total, LDL, HDL, TG) mmol/L | | | | | |
| Apolipoproteins (A-I, A-II, B etc.) | | | | | |
| Muscle biochemistry | | | | | |
| Citrate synthase activity ($\mu\text{mol}\cdot\text{g}^{-1}\cdot\text{min}^{-1}$) | | | | | |
| 3-HAD activity ($\mu\text{mol}\cdot\text{g}^{-1}\cdot\text{min}^{-1}$) | | | | | |
| PFK activity ($\mu\text{mol}\cdot\text{g}^{-1}\cdot\text{min}^{-1}$) | | | | | |
| Clinical and patient- reported | | | | | |

| | | | | | |
|------------------------------|--|--|--|--|--|
| SF-36 (total and subdomains) | | | | | |
| SAMS scores (0–10) | | | | | |

Section 6: Analysis

26. Outcome definitions

Primary outcome

- *Citrate-synthase maximal activity* ($\mu\text{mol}\cdot\text{g}^{-1}\cdot\text{min}^{-1}$), measured in skeletal-muscle homogenates by fluorometry.

The primary endpoint is the change from baseline (V1) to 12-week follow-up (V2).

Key secondary outcome

- *Maximal oxygen uptake (VO_{2peak})* ($\text{mL}\cdot\text{kg}^{-1}\cdot\text{min}^{-1}$), assessed during an incremental cycling test to exhaustion.

The key secondary endpoint is the change from V1 to V2.

Additional secondary outcomes

Unless otherwise specified, outcomes refer to the within-participant change (V2 – V1).

They include (but are not limited to) variables in the following domains:

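### Section 30 pools spontaneous and questionnaire-elicited adverse events in one count, although scheduled contact differs widely between exercise and non-exercise arms, so that comparison is open to ascertainment bias

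*SAP*

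**What the plan says.** Section 30 (Harms) fixes how events are counted: "All reported events will be summarized descriptively by intervention group according to" frequency, severity and assessed relationship to the intervention. Frequency is the number and share of participants with at least one AE. It is not split by how the event came to light. Two sources feed it, spontaneous reports and questionnaires such as a structured SAMS inventory. The questionnaires, the section says, "will supplement spontaneous reports to ensure standardized data collection". No formal testing of harms is planned.

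The contact schedule is set elsewhere in the SAP. Section 9 gives the exercise arms "Supervised high-intensity interval training (HIIT) three times per week", and the adherence definition in Sections 19–20 repeats "3 sessions/week planned". The trial runs "over 12 weeks in adults with dyslipidaemia". After randomization, the visits listed for all arms are "Week 6 = mid-intervention blood samples and questionnaires" and then V2 at 12 weeks. The non-exercise arms are told only to keep their usual activity. Section 15 places questionnaires at V1, week 6 and V2, with no difference by arm.

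SAMS also appears outside Section 30. A 0–10 score is among the baseline variables in Table 1, and SAMS severity and type is a secondary outcome in Section 26, where outcomes are by default the change from V1 to V2.

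**The concern.** The questionnaire is scheduled equally in all arms, but the opportunity to report spontaneously is not. A participant who meets staff three times a week has many more occasions to mention an ache, a strain or a cold than one who is seen twice in 12 weeks. Once both sources go into one yes/no count per participant, the count carries that inequality, and the claim of standardization no longer holds for it.

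The SAP's overall objective covers the separate and combined effects of atorvastatin and exercise, so a four-column AE table will be read across columns. A natural question is whether adding training to atorvastatin brings more muscle symptoms than atorvastatin alone, and the pooled count is open to distortion on exactly that comparison. Section 30 also allows exploratory summaries by adherence status. In the exercise arms adherence includes attendance, so better adherers have more chances to report.

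A smaller, related gap is that Section 30 does not say how a muscle complaint already present at V1 is counted when it is reported again at week 6 or V2.

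**Working it through.** The SAP states no AE rate, capture rate or contact count, so there is no harms figure to reproduce.

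**Scheduled contacts after randomization (from the SAP)**

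| | Exercise arms | Non-exercise arms |
|---|---|---|
| Supervised sessions | 3 × 12 = 36 | 0 |
| Week 6 and V2 | 2 | 2 |
| Total | 38 | 2 |
| Total at 75% attendance | 0.75 × 36 + 2 = 29 | 2 |

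The questionnaire alone is scheduled 2 against 2.

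**Illustration A: fixed capture (all rates assumed).** Observed share = true share × probability of capture. Take a true share of 30% in both and 90% capture in the exercise arms, so 0.30 × 0.90 = 27.0%.

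| Non-exercise capture | Non-exercise observed | Difference (points) | Ratio |
|---|---|---|---|
| 90% | 27.0% | 0 | 1.00 |
| 80% | 24.0% | 3 | 1.13 |
| 70% | 21.0% | 6 | 1.29 |
| 60% | 18.0% | 9 | 1.50 |
| 50% | 15.0% | 12 | 1.80 |

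The ratio does not depend on the true share; the difference scales with it. At a true share of 40%, capture of 80% down to 50% gives 36% against 32% down to 20%, a gap of 4 to 16 points.

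**Illustration B: forgetting between contacts (assumed).** Events fall evenly over 84 days, and each is captured at the next contact with probability exp(−lag/τ). With contacts at days 42 and 84 only, mean capture is (τ/42) × (1 − exp(−42/τ)). The exercise figures are simulated with three sessions a week on fixed days. The mean wait to the next contact is about 1.2 days against 21 days.

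| τ (days) | Exercise capture | Non-exercise capture | Ratio |
|---|---|---|---|
| 14 | 0.921 | 0.317 | 2.91 |
| 28 | 0.960 | 0.518 | 1.85 |
| 56 | 0.979 | 0.704 | 1.39 |
| 112 | 0.990 | 0.834 | 1.19 |

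Both illustrations set the true difference to zero, so the whole ratio is artefact. They show a direction and a plausible range, not an estimate for this trial.

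**Baseline complaints (assumed).** Suppose 25% have muscle symptoms at V1, a share r of these is counted as on-intervention SAMS, and new SAMS occurs in p of everyone else. The tabulated share is 0.25r + (1 − 0.25r)p. With p = 20% on atorvastatin and 10% on placebo:

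- r = 0: 20% against 10%, ratio 2.00
- r = 0.5: 30% against 21.25%, ratio 1.41
- r = 1: 40% against 32.5%, ratio 1.23

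Section 30 does not fix r.

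**The case against.** **The protocol is not shown.** How AEs are elicited, and whether non-exercise participants are telephoned or seen for drug supply, is commonly left to it. Section 9 lists study visits, not necessarily every contact. The SAP does not say that AEs are asked about at training sessions. This stands, and it limits the claim. A reader might infer that the comparison is biased, or that any excess in the exercise arms merely reflects more frequent asking. The SAP supports neither statement, only that the pooled count is open to bias. How events are pooled and tabulated, however, belongs to the SAP, and Section 30 settles that.

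**Harms are descriptive and untested.** True, so no test is invalidated. The effect is on how the table is read. The trial's main contrast, Exercise + Placebo against Exercise + Atorvastatin, has equal scheduled contact and blinded medication.

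**SAMS already has a baseline-referenced analysis.** As a secondary outcome it is analysed as V2–V1 on the same schedule in every arm. A reader might infer that Section 30 counts pre-existing complaints as new SAMS. It does not say so: monitoring starts with the intervention, events can be classed as unrelated, and no rule turns a 0–10 score into an AE. On this point Section 30 is silent, which is less than wrong.

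**Relying on the questionnaire alone would lose information.** It is tempting to base every exercise versus non-exercise comparison on the structured inventory. The only inventory the SAP names covers muscle symptoms, so injuries and other non-muscle events tied to training would drop out. That objection stands, and the fix below avoids it.

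**Conclusion.** The point holds in a limited form. Section 30's single AE frequency combines an equally scheduled source with one that has far more opportunity in the exercise arms: 38 scheduled contacts against 2, assuming that the protocol adds none for the non-exercise arms. The statement that questionnaires standardize data collection is therefore not right for the pooled count. Exercise versus non-exercise AE and SAMS frequencies are open to ascertainment bias, probably upward in the exercise arms.

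The size cannot be derived from the SAP. Under the assumed capture rates in illustration A, the spurious ratio runs from 1.00 to 1.80. It would be near 1 if essentially every event is captured at week 6 and V2. Unequal contact does not affect atorvastatin versus placebo within the same exercise allocation.

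The treatment of complaints present at V1 is a secondary gap in wording, partly covered by the change-from-baseline outcome, and best closed in the same edit.

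**What to change.** In Section 30:

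1. Tabulate questionnaire-elicited events (week 6 and V2, same schedule in all arms) separately from spontaneous or session-reported events, and confine the statement about standardized collection to the questionnaire data.
2. Make the questionnaire table the main basis for reading SAMS across exercise and non-exercise arms.
3. Count a questionnaire SAMS as on-intervention only if it is new or worse than that participant's V1 report, in line with the V2–V1 definition in Section 26.
4. Keep all other AEs, including non-muscle and training-related events, in the by-arm tables, with a stated caveat that contact frequency differs between exercise and non-exercise arms.

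The cost is one extra table and a few sentences, with no new data collection. It relies on being able to separate questionnaire data from other AE reports. If that cannot be done, the caveat in item 4 should cover the whole AE summary. Spontaneous events remain unequally ascertained across exercise allocation even after the split, which is why the caveat is needed.
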